Specific Aim 2: The distributional nature of all variables will be assessed, and nonparametric tests (e.g., Fisher's Exact Test; Mann-Whitney test), data transformations (e.g., log linear), or other alternate methods (e.g., weighted least squares regressions) will be conducted where appropriate. First, we will compare baseline demographic, clinical, and patient-centered variables (including medication use) between EPIC and EUC with chi-square and independent samples t-tests. Variables with p-values  $< 0.25$  will be included as control variables or propensity scores in subsequent models. We will then compare baseline demographic, clinical, and patient-centered variables between those who complete the study and those who do not using chi-square and independent samples t-tests. Outcome analyses at both post-intervention and post-maintenance will be intention-to-treat and will use the multiple imputation procedures Proc MI and MINANALYZE in SAS Version 9.3 to estimate missing observations. We will evaluate the degree of dependency between patients within a given group session, between patients in a given PACT, and between PACTs within each of the five sites (by examining Intra Class Coefficients). It is likely that significant dependency will exist, and if so, we will accordingly take these into account in analyses (i.e., patients will be nested within PACTs which will in turn be nested within sites). Random regression methods using SAS Proc Mixed will be employed to account for clustering of data.

5.6.C.i. H2 Analyses (Effectiveness) We will employ Analysis of Covariance (ANCOVA) to examine treatment differences in outcomes immediately post-intervention (at 4 months). We will conduct two models: one with HbA1c at post-intervention as the outcome and one with DDS at post-intervention as the outcome. Models will include treatment group (i.e., EPIC versus EUC) as a predictor and respective HbA1c and DDS baseline scores and any demographic,

clinical, or patient-centered variables that differed between the study arms at baseline as covariates. We will calculate treatment effect sizes immediately post-intervention.

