5.6.C.ii. H3 Analyses (Maintenance) Analyses for examination of maintenance of treatment effects will be similar to those for immediate treatment effects post-intervention. We will again employ ANCOVA to examine treatment differences in outcomes at the post-maintenance (10-month) assessment. We will conduct two models: one with HbA1c at 10-months as the outcome and one with DDS at 10-months as the outcome. Models will include treatment group (EPIC versus EUC) as a predictor and respective HbA1c and DDS post-intervention scores and any demographic, clinical, or patient-centered variables that differed between the study arms at baseline as covariates. We will calculate treatment effect sizes at the 10-month assessment.

5.6.C.iii. Exploratory Analyses (Implementation and Effectiveness) We will use a mixed-model approach to conduct separate repeated-measures analyses for HbA1c and DDS simultaneously using all three assessment time points. We will employ growth curve analyses using SAS Proc Mixed to examine overall group differences in improvements or decrements in outcomes over the year, maximize participant data, and account for dependency between patients within a given group session, PACT, and site. Conditional models will contain fixed terms for the intercept, treatment (EPIC or EUC), assessment time period, treatment by time period interaction, and previously identified variables that differ between treatment groups. Modeled random effects will include between-patient variation in baseline scores (i.e., the intercept where baseline assessments are scored 0) and variation in the slopes for time. With three assessments, the focus will initially be on linear patterns of change, although we will evaluate the relative fit of a quadratic pattern of change using the likelihood ratio test. These analyses will allow us to examine the immediate impact of treatment at post-intervention as well as retention, improvement, or decay in outcomes post-maintenance period. The treatment effect will assess differences between the two groups at baseline, the fixed effect of time will measure the average change over time in the outcome (collapsing across the two treatment groups), and the time by treatment interaction will indicate whether change over time (in slopes) differs between EPIC and EUC.

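### The H2 and H3 analyses do not settle whether the EPIC group is modelled: dependency enters if "significant", with no criterion, and no EPIC-group random effect is written out anywhere

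*Combined protocol and SAP*

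**What the plan says.** All places are in the combined protocol and SAP.

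- **5.6.C, Specific Aim 2, levels examined:** "We will evaluate the degree of dependency between patients within a given group session, between patients in a given PACT", and also between PACTs within sites, by looking at ICCs.
- **Same paragraph, condition:** "It is likely that significant dependency will exist, and if so, we will accordingly take these into account in analyses". No test, significance level or ICC threshold is given. The structure then spelled out is "i.e., patients will be nested within PACTs which will in turn be nested within sites".
- **Same paragraph, next sentence:** "Random regression methods using SAS Proc Mixed will be employed to account for clustering of data". This has no condition, but it names no level.
- **5.6.C.i (H2):** an ANCOVA. "Models will include treatment group (i.e., EPIC versus EUC) as a predictor and respective HbA1c and DDS baseline scores", plus covariates that differ at baseline. No random effect is listed.
- **5.6.C.ii (H3):** the same form at 10 months. "Models will include treatment group (EPIC versus EUC) as a predictor and respective HbA1c and DDS post-intervention scores", plus the same covariates. Again no random effect is listed.
- **5.6.C.iii (exploratory growth model):** one stated aim is to "account for dependency between patients within a given group session, PACT, and site". The random effects it then lists are only the patient intercept and the time slope.
- **Design:** randomization is by patient (5.1.A, 5.1.D.iv). About 12 patients per PACT go to either arm, from 24 PACTs (5.6.A). EPIC groups have 5 to 8 members and are meant to stay together (5.1.E.iii). EUC patients have no EPIC groups (5.1.A).

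**The concern.** Two analysts following this text in good faith could fit different models to the same primary comparison. One could stop at the written nesting of PACT and site. The other could add the EPIC group if its ICC looked large enough. They would report different standard errors for HbA1c and DDS, and the choice would follow a look at the data.

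The level left open is the one that matters for this contrast. Both arms are drawn from each PACT, so an effect shared by all patients of a PACT largely cancels from the difference (not exactly, since allocation is not described as stratified by PACT). The EPIC group sits in one arm only. Its members share a leader, sessions and intended peer support, so any group effect adds to the variance of the EPIC mean and is not offset in EUC. If it exists and is left out, the standard error is too small and the two-sided test rejects more than 5% of the time.

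**Working it through.** **1. The plan's own figure (5.6.A).** Inputs: d = 0.40, two-sided alpha 0.05, 80% power.
- n per arm = 2 × ((1.960 + 0.842)/0.40)² = 98.1, so 99. The plan uses 100, which gives 80.7% power.
- PACT design effect: 1 + (12 − 1) × 0.0183 = 1.2013, and 100 × 1.2013 = 120.
- Attrition of 15%: 120/0.85 = 141.2, so 142 per arm and 284 in total.

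The 284 reproduces. It contains no allowance for EPIC groups.

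**2. Group left out of the model.** Let m be the number analysed per EPIC group, n the number analysed per arm, and ρ the group ICC of the adjusted outcome. The true variance of the difference is proportional to {[1 + (m − 1)ρ] + 1}/n. The model without groups uses 2/n. Hence:
- inflation I = [2 + (m − 1)ρ]/2
- standard-error factor = √I
- actual alpha = 2[1 − Φ(1.96/√I)]

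Groups of 5 to 8 less 15% attrition give m = 4.25 to 6.8. The documents give no group ICC, so ρ = 0.01 to 0.10 is assumed. The value 0.0183 is the plan's PACT ICC, used only as a reference point.

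| ρ | m = 4.25: I, √I, alpha | m = 6.8: I, √I, alpha |
|---|---|---|
| 0.01 | 1.016, 1.008, 5.2% | 1.029, 1.014, 5.3% |
| 0.0183 | 1.030, 1.015, 5.3% | 1.053, 1.026, 5.6% |
| 0.05 | 1.081, 1.040, 5.9% | 1.145, 1.070, 6.7% |
| 0.10 | 1.163, 1.078, 6.9% | 1.290, 1.136, 8.4% |

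**3. Group added only after a test.** For k groups of m, a one-way random-effects F-test at 5% detects ρ with probability P(F > F_crit/[1 + mρ/(1 − ρ)]), on k − 1 and k(m − 1) degrees of freedom. Take 120 EPIC patients as 24 groups of 5, 20 of 6 or 15 of 8:
- ρ = 0.05 is detected 19%, 21% and 25% of the time.
- ρ = 0.10 is detected 41%, 45% and 51% of the time.

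A simulation shows what this does to alpha. Its settings are 284 patients, 24 PACTs in 5 sites, a PACT ICC of 0.0183 common to both arms, 15% random attrition, Satterthwaite degrees of freedom, a likelihood-ratio trigger, and 4,400 trials per cell (Monte Carlo SE 0.3 to 0.4 points). Rejection rates in %:

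| Assigned per group, ρ | Never modelled | If p < 0.05 | If p < 0.25 | Always modelled |
|---|---|---|---|---|
| 6.5, 0 | 4.8 | 4.8 | 4.6 | 4.4 |
| 6.5, 0.0183 | 6.2 | 5.9 | 5.4 | 5.1 |
| 6.5, 0.05 | 6.5 | 5.9 | 5.0 | 4.8 |
| 6.5, 0.10 | 7.6 | 6.1 | 5.1 | 4.9 |
| 8, 0.05 | 7.3 | 6.3 | 5.5 | 5.1 |
| 8, 0.10 | 9.2 | 7.1 | 5.8 | 5.4 |

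Two "never modelled" cells lie about two Monte Carlo SEs above the formula: 6.2% against 5.5% (m = 6.5 × 0.85 = 5.525, ρ = 0.0183), and 9.2% against 8.4% (m = 6.8, ρ = 0.10). The formula figures are therefore approximate.

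**4. H3.** This model conditions on the 4-month score, so its inflation depends on how group effects persist. At ρ = 0.10, 6.5 assigned per group and an assumed individual 4-to-10-month correlation of 0.6, never modelling the group gives a simulated alpha of 5.4% if group effects persist fully, and 7.8% if they persist like individual scores. The documents fix neither assumption.

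**5. Is 284 enough?** With 120 analysed per arm and PACT effects common to both arms, 80% power at d = 0.40 needs 2 + (m − 1)ρ ≤ 0.16 × 120/(1.960 + 0.842)² = 2.446, so (m − 1)ρ ≤ 0.446. The tolerated ICC is 0.446/5.8 = 0.077 at m = 6.8, and 0.446/3.25 = 0.137 at m = 4.25.

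**The case against.** The best defence is that the plan does intend to handle the group. Group session comes first among the levels to be examined, the text calls dependency likely, what will be taken into account can be read to include the group, and the Proc Mixed sentence is unconditional. This stands against one stronger reading: a reader might infer that the plan omits group clustering from H2 and H3, or ignores clustering altogether. The documents do not say that. They leave it open, because the unconditional sentence names no level and the only nesting written out stops at PACT and site.

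A reader might also infer that 5.6.C.iii already commits to a group term, so that H2 and H3 need only be brought into line with it. It states the aim, but its listed random effects contain no group.

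The size can be contested too, and much of that stands. At ICCs of 0.01 to 0.02 the inflation is small. The 5% trigger is an assumption. The only numeric screening level in 5.6.C is p < 0.25, for covariates and predictors, and with that trigger the simulated alpha is 5.0% to 5.8% for the non-zero ICCs tried. A formula alpha of 9.2% needs 8 analysed in every group at an ICC of 0.10, which does not fit a cap of 8 with 15% attrition.

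Finally, a reader might infer that the trial is too small. Step 5 does not show that.

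**Conclusion.** The concern holds as a gap in pre-specification that bears on the type I error of both primary outcomes. It should be fixed, but it does not undermine the design.

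If the written nesting is followed, alpha by formula is about 5.2% to 8.4% over assumed group ICCs of 0.01 to 0.10, and about 5.3% to 5.6% at 0.0183. A significance gate reduces the excess but does not reliably remove it: at 5% it would miss a group ICC of 0.05 in 75% to 81% of trials, while a looser gate brings alpha close to nominal. The H3 size cannot be fixed from the documents.

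These figures rest on an assumed group ICC, equal group sizes, random attrition and PACT effects common to both arms. Confidence is medium: the textual gap is certain, and its numerical effect is not.

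**What to change.** - **5.6.C, 5.6.C.i and 5.6.C.ii:** replace the conditional rule with a pre-specified Proc Mixed random effect for assigned EPIC group, in the EPIC arm only, with EUC patients as singletons. Include it whatever the observed ICC, use Satterthwaite or Kenward-Roger degrees of freedom, keep PACT and site in the model, and let the residual variance differ by arm.
- **Group membership:** the plan says "Outcome analyses at both post-intervention and post-maintenance will be intention-to-treat", so define the group by assignment at scheduling. Non-attenders and switchers stay in their assigned group. EPIC patients never scheduled to a group are singletons.
- **5.6.C.iii:** add the same group term to the listed random effects.
- **Optional, 5.6.A:** say that the PACT design effect of 1.2013 is the factor for randomizing whole PACTs and is not needed for a comparison within PACTs. This holds only if the treatment effect does not vary by PACT. Give the group ICC that the sample tolerates (about 0.08 to 0.14).

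**Cost:** SAP wording, one random-effect line, and an assigned-group identifier for each scheduled EPIC patient. Standard errors are about 1% to 14% larger over the assumed ICCs, and the test is slightly conservative if the ICC is zero (4.4% simulated). N stays at 284. Leaders or individual session providers shared across groups (5.1.D) are a further level that this term does not cover and that is not quantified here.

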#### **5.2.B.i. Identification of Patient- Participants and Recruitment Strategies.**

- 1) Identify potentially eligible patient-participants in VISN 12 and Houston using data from the Corporate Data Warehouse. To ensure accurate ascertainment of diabetes diagnosis, we will identify patients with at least 2 outpatient or 1 inpatient ICD-9 code for diabetes mellitus. We will extract HbA1c values from the prior 6 months. Patients with mean HbA1c  $\geq$  8.0% will be eligible for Step 2.
- 2) We will perform a standardized medical-record review to verify the diagnosis of diabetes and evidence of any exclusion criteria. We will use a step-wise approach to the medical-record review, adapted from our prior work, in blocks of 100 patients. Patient blocks will be organized by PACT team. We will send opt-out letters (Attachment 15) to patients that remain eligible for study participation. To ensure timely responses to patients and realistic work load, opt-out letters will not be sent until we have attempted to contact 3/4ths of the prior block sample.
- 3) We will then recruit all potentially eligible patients via an opt-out letter sent on behalf of the PACT team mailed to their home address. Letters written at a sixth-grade reading level will direct patients to call an opt-out number if they do not wish to be contacted about the study. A toll-free telephone number answered by voice mail will be available for those with questions or who want to leave an opt-out message. Unless the patient requests that he/she not be contacted, research personnel will contact the patient after ten days or after the first telephone response from the same batch of letters is received, whichever comes sooner. This protocol was previously approved by VA Institutional Review Boards.
- 4) We will then call potential subjects to introduce the study objectives and procedures and to obtain verbal consent to administer a screening protocol. All potential participants who express interest in the study and who do not meet the exclusion criteria will be invited to a group introductory meeting. Time permitting, a letter detailing the date, time and location of the introductory meeting will be mailed to the patient (Attachment 16). Research staff will provide a reminder call to invited patients before the introductory meeting to ensure adequate group numbers and to answer any remaining questions or concerns in a private conversation.

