#### **5.5.B. Data Collection Strategy § 5.1.H.**

#### **5.5.C. Study Variables § 5.1.I.**

### **5.6 Data Analysis**

#### **5.6.A. Sample Size Calculation/Sample size determination**

Sample size is calculated according to the estimated intervention effect size at post-intervention. We then estimate power to detect treatment effects at the post-maintenance (10-month) follow-up as well as power to detect treatment differences in linear change across the three time points for a 3-level cluster-randomized trial with repeated assessments. We will adjust models for baseline covariates of study patients. All tests will be two-sided with an alpha of 0.05. In our recent RCT, differences in HbA1c change between EPIC versus enhanced group education indicated medium treatment effects at post-treatment and at 1-year (Cohen's  $d = 0.48$  and  $0.42$ , respectively). A similar trial revealed a treatment difference between a glucose self-monitoring protocol and an active control group in DDS scores that correspond to large effects of treatment at 1-year (all pre-post  $d$ s  $> 0.80$ ). To capture treatment effects for both clinical and patient centered outcomes in this implementation trial, a conservative small-to-medium effect size of  $d = 0.40$  (which is 16.67% smaller than the effect found for HbA1c in the prior trial) was used to calculate sample size. Assuming no intra-class correlation (ICC) within

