PACTs, 100 patients in each treatment arm (i.e., EPIC and EUC) will allow for 80% power to detect small-to-medium effects and 98% power to detect medium effects ( $d = 0.50$ ). To account for the dependency among patients within a PACT, the Design Effect (Deff) was applied, following the approach of Schnurr et al. The sample size was inflated using the formula,  $Deff = 1 + (n-1)\rho$ , where  $n$  is the average number of patients per PACT and  $\rho$  is the ICC for PACTs. In our preliminary work, we identified an ICC for PACTs of 0.0183, an average of 27 eligible patients per PACT, and expect that an average of 12 patients per PACT will participate, which yields  $Deff = 1 + (12-1) * 0.0183 = 1.2013$ . Applying this adjustment, the minimum number of patients in the clustered design is  $100 \times 1.2013 = 120$  in each treatment group. Further adjusting for a maximum of 15% attrition, 142 patients will be recruited for each treatment group (total  $N = 284$ ). Therefore, the minimum number of PACTs to be sampled for this nested analysis is technically 11.8, (i.e.,  $142/12$ ), which will be rounded up to 24 PACTS. This is highly feasible, representing just 32.5% of the total number of PACTs (75) at all study sites. Treatment group effect sizes as small as  $d = .40$  can be detected with 80% power at 1-year given a total of 284 patients (an average of approximately 12 patients randomized to either EPIC or EUC from within 24 PACTs sampled), even after accounting for maximum attrition and estimated dependency within PACTs. A sample size of 284 participants is adequate for repeated measures analyses as well. Optimal design software estimated power to detect treatment group differences in linear change across all three assessments. Prior data indicated a main effect of treatment (EPIC versus enhanced group education) for linear change in HbA1c of 0.20, and between – and within – PACT variance in linear change of 0.018 and 0.206, respectively. These values indicate a small-to-medium between-groups effect size of 0.42. A total of 284 participants allows for 80% power to detect a slightly larger effect size ( $\delta = .53$ ) for repeated measures analyses of linear change over time. Furthermore, there is 98% power to detect a medium effect size of  $\delta = .75$ .

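### Free precision gain: fix the screening HbA1c mean as a second covariate in the H2 HbA1c model instead of leaving its entry to chance imbalance between arms

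*Combined protocol and SAP*

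**What the plan says.** Two separate HbA1c values exist before randomization.

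- **Screening mean.** Section 5.2.B.i, step 1, states "We will extract HbA1c values from the prior 6 months", and only patients whose mean is at least 8.0% go forward. Sections 5.2.B and 5.4.B give the same entry rule.
- **Baseline draw.** Under step 6 of Section 5.2.B.i, a new sample is taken after consent. A patient whose result is below 7.5% is withdrawn and not randomized.

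Table 10 lists HbA1c separately under Screen and Baseline. DDS has no Screen entry.

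For H2, Section 5.6.C.i specifies an ANCOVA: "Models will include treatment group (i.e., EPIC versus EUC) as a predictor and respective HbA1c and DDS baseline scores". It also admits demographic, clinical or patient-centered variables that differed between arms at baseline, and Section 5.6.C sets that screen at p < 0.25. The screening mean is not named there, in the growth model, or in the text on multiple imputation. Its only stated use is eligibility.

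**The concern.** HbA1c is a primary outcome, and an earlier reading of it is an obvious candidate predictor of the 4-month value. Here that reading is already extracted, and the entry rule makes it complete: a patient with no value in the window cannot have a mean of at least 8.0%.

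As written, the mean could reach the H2 model only through the arm-difference screen. Under randomization a variable passes a p < 0.25 screen about one time in four, whether or not it predicts the outcome. So its use would depend on chance imbalance and not on what it adds.

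What is at stake is the width of the confidence interval for EPIC versus EUC on HbA1c. The sample size has little slack, and Section 5.1.C records that Houston was added because of concern about staffing at the VISN 12 sites. Precision that needs no extra patients is therefore worth having, if there is enough of it.

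**Working it through.** **1. The plan's own figure (Section 5.6.A).** Inputs: "All tests will be two-sided with an alpha of 0.05"; "a conservative small-to-medium effect size of" d = 0.40; 100 per arm, which "will allow for 80% power to detect small-to-medium effects"; "we identified an ICC for PACTs of 0.0183"; "expect that an average of 12 patients per PACT will participate"; 15% attrition; 1:1 allocation.

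- Per arm, unclustered: 2 × ((1.960 + 0.842)/0.40)² = 98.1, so 99 (99.1 with the t distribution; the plan uses 100).
- Design effect: 1 + 11 × 0.0183 = 1.2013, giving 120 per arm.
- Attrition: 120/0.85 = 141.2, so 142 per arm and 284 in total. This reproduces.
- Effective size: 142 × 0.85/1.2013 = 100.5 per arm.
- Power: Φ(0.40 × √(100.5/2) − 1.960) = Φ(0.875) = 80.9%.

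**2. Formula for the gain.** Let rb, rs and rsb be the baseline–outcome, screening–outcome and screening–baseline correlations among enrolled patients.

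- R² with both readings = (rb² + rs² − 2·rb·rs·rsb)/(1 − rsb²).
- Residual variance ratio, both readings against baseline only = (1 − R²)/(1 − rb²).
- Patient equivalent = 284/ratio − 284.
- Power = Φ(0.40 × √(100.5/(2 × ratio)) − 1.960), taking d = 0.40 on the baseline-adjusted residual SD.

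**3. Assumptions.** The documents give neither an HbA1c SD nor any between-visit correlation. I simulated trivariate-normal values (screening, baseline, outcome) with source mean 7.6 and SD 1.6. I kept those with screening at least 8.0 and baseline at least 7.5, then applied the formula to the correlations that remained.

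| Assumed source correlations: screen–baseline / baseline–outcome / screen–outcome | Variance reduction | Patient equivalent | Power |
|---|---|---|---|
| 0.75 / 0.65 / 0.50 | 0.04% | 0.1 | 80.9% |
| 0.65 / 0.65 / 0.45 | 0.1% | 0.3 | 81.0% |
| 0.80 / 0.65 / 0.55 | 0.25% | 0.7 | 81.0% |
| 0.65 / 0.65 / 0.50 | 0.9% | 2.5 | 81.3% |
| 0.65 / 0.65 / 0.55 | 2.4% | 7 | 81.9% |
| 0.65 / 0.65 / 0.65 | 8.3% | 26 | 84.2% |

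**4. The best case by hand.** After the cut-offs, rb = 0.43, rs = 0.41 and rsb = 0.39.

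- R² = (0.185 + 0.168 − 0.138)/0.848 = 0.254.
- Ratio = 0.746/0.815 = 0.915 (0.917 before rounding).
- Patients: 284/0.917 − 284 = 25.7.
- Power: Φ(0.40 × √(50.24/0.917) − 1.960) = Φ(1.00) = 84%.

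**5. Limits of the range.** If the older value carries information only through the baseline value (rs = rb × rsb), the ratio is exactly 1 and nothing is gained. A higher assumed source mean of 8.5, with all three correlations at 0.65, gives a reduction of about 10%.

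**6. Scale of d.** The prior effect sizes concern HbA1c change ("differences in HbA1c change between EPIC versus enhanced group education indicated medium treatment effects"), with no SD given. If d = 0.40 is instead on the unadjusted SD, baseline adjustment already lifts power. In the best case it goes from Φ(0.40 × √(50.24/0.815) − 1.960) = 88% to Φ(0.40 × √(50.24/0.747) − 1.960) = 91%, a smaller step.

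**The case against.** The strongest reply is that nothing here is wrong. A baseline-adjusted ANCOVA is standard and valid, 284 reproduces without the extra covariate, and one can always propose another prognostic variable. The gain is mostly small: it reaches 8% only if an older chart average predicts the 4-month value as well as the fresh draw does. The mean is also uneven, since the number and age of the values behind it vary by patient, as does the gap to the baseline draw. All of this stands. It limits the size of the point but does not remove it, because the value is in hand and using it costs almost nothing.

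A reader might infer more than the documents support in four ways.

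- *That the planned estimate is biased, or the trial underpowered.* It is neither on this ground: treatment is randomized, and the stated power is met without the covariate.
- *That the 7.5% cut-off spoils the baseline draw and so calls for a second reading.* The screening mean is cut harder, at 8.0%. With source correlations 0.65/0.65/0.45, selection takes baseline–outcome from 0.65 to about 0.48, but screening–outcome from 0.45 to about 0.22.
- *That the gain is 15% to 17%, with power up to 87.5%.* Those figures need equal correlations of 0.7 (cut-offs ignored) or 0.8 (cut-offs applied) among all three readings, and the documents give no basis for that.
- *That the imputation model leaves the screening mean out.* Section 5.6.C lists no imputation variables at all, so it is unspecified, not excluded.

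**Conclusion.** The point holds as a free improvement to the H2 HbA1c analysis. A complete pre-randomization reading of the outcome is available, and the plan would use it only if the arms happened to differ on it. On the assumptions in the working, fixing it in advance cuts residual variance by about 0% to 8%, equal to 0 to about 26 patients at N = 284. Power moves from about 81% to at most about 84%, with d = 0.40 on the baseline-adjusted residual SD. Expect a few patients' worth. The upper end needs the older mean to predict as well as the fresh draw, and the gain vanishes under first-order decay. The range rests on assumed SD and correlations, so the documents alone cannot fix the gain. The point does not extend to DDS and implies no bias.

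**What to change.** In Section 5.6.C.i, add one sentence: the H2 HbA1c model will include, as fixed covariates whatever the arm balance, both the post-consent baseline HbA1c draw and the screening HbA1c mean (Corporate Data Warehouse, prior 6 months). Because the screening mean is then part of the analysis model, list it in the PROC MI model for HbA1c as well. The DDS model is unchanged.

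The cost is one sentence and one degree of freedom out of roughly 241 patients with outcome data (284 × 0.85). No extra data collection is needed, since the value is already extracted for screening. The change should be made before outcome data are seen; added later, it could look like covariate selection.

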**Table 5. RE-AIM Elements and Corresponding Measures**

RE-AIM Elements (Phase 2)	Proposal's Corresponding Measures
Reach: Representativeness of patients who are willing to participate in the intervention	Characteristics of enrolled study participants from a given PACT patient panel compared to those of all PACT patients meeting eligibility criteria from that panel
Effectiveness: Intervention's impact on important outcomes, including negative effects like diabetes distress	Differences in HbA1c and DDS between EPIC and EUC study arms at 4 months (post-intervention)
Adoption: Representativeness of settings & intervention agents willing to initiate a program and their actual use of program or intervention components	
 
1) Characteristics of PACT teams with participating members
 
2) Timing and frequency of one-on-one sessions following each group sessions
 

Implementation: The intervention agents' fidelity to the various elements of an intervention's protocol; patients' use of the intervention strategies; and the costs and cost-effectiveness of the intervention	
 
1) Proportion of group sessions attended (out of six) for each enrolled patient
 
2) Proportion of individual sessions attended (out of six) for each enrolled patient
 
3) Objective ratings of individual session providers' fidelity to the collaborative goal-setting methodology using a structured fidelity rating process completed by a behavioral coaching expert on the study team
 
4) Patients' perceptions of goal-setting engagement by providers in both the intervention and EUC arms
 
5) Objective ratings of goal and action plan quality using our validated GET-D tool by trained research staff blinded to random assignment
 
6) Cost-utilization and cost-effectiveness of EPIC compared with EUC arms.
 

Maintenance: Long-term effects of a program on outcomes 6 or more months after the most recent intervention contact	Differences in HbA1c and DDS between EPIC and EUC study arms to measure intervention persistence at 10 months

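### The H3 model adjusts the 10-month outcome for the post-intervention score instead of baseline, so it does not estimate the EPIC versus EUC difference at 10 months

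*Combined protocol and SAP*

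**What the plan says.** The target is the same wherever the plan describes maintenance. H3 in the Abstract (0.0.2) states that EPIC patients will maintain significant improvements in HbA1c and DDS at 10 months compared with enhanced usual care. Section 3.0 gives the same hypothesis but calls the visit 1-year. The Maintenance row of Table 5 defines the measure as "Differences in HbA1c and DDS between EPIC and EUC study arms to measure intervention persistence at 10 months". The opening of 5.6.C.ii says that ANCOVA will examine treatment differences at the 10-month assessment, and its last sentence promises effect sizes at that time.

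The H2 model (5.6.C.i) adjusts the 4-month outcome for "respective HbA1c and DDS baseline scores". The H3 model is introduced as similar, but its text is: "Models will include treatment group (EPIC versus EUC) as a predictor and respective HbA1c and DDS post-intervention scores". No reason is given for the change of covariate. Other covariates enter only if they differed between arms at baseline.

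Section 5.6.A claims that effects as small as d = 0.40 "can be detected with 80% power at 1-year given a total of 284 patients".

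**The concern.** H2 predicts that treatment moves the 4-month score. Holding that score fixed removes from the 10-month comparison the part of the effect that the 4-month score already carries. What remains is not the 10-month difference. Nor is it protected by randomization, because patients with equal 4-month scores are compared across arms after treatment has shifted those scores.

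The plan's own mediation analysis (5.6.C.iii) has this structure. Its third model adds a post-randomization variable alongside treatment in order to separate out an indirect effect. H3 does the same thing with the 4-month outcome but presents the result as the treatment difference at 10 months.

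HbA1c and DDS are the two primary outcomes, and H3 is one of two Aim 2 hypotheses. A programme whose benefit lasts could fail its maintenance test, and one whose benefit partly fades could appear harmful.

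**Working it through.** Effects are in SD units, and positive values favour EPIC.

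**Inputs from 5.6.A.**
- Test level: "All tests will be two-sided with an alpha of 0.05".
- Design effect size: "a conservative small-to-medium effect size of" d = 0.40.
- Prior-trial HbA1c differences that "indicated medium treatment effects at post-treatment and at 1-year": 0.48 and 0.42.
- Unclustered size: "100 patients in each treatment arm (i.e., EPIC and EUC) will allow for 80% power to detect small-to-medium effects".
- ICC 0.0183, 12 patients per PACT, 15% attrition, 142 recruited per arm.

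**Assumed, because the documents do not give them.** The within-arm correlation ρ between 4- and 10-month scores is taken from 0.3 to 0.9, with equal SDs at the two visits.

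**Step 1: the plan's own figure.**
- Required n per arm = 2(1.960 + 0.842)²/0.40² = 98.1, so 99. The plan uses 100.
- Power at 100 = Φ(0.40/√(2/100) − 1.960) = Φ(0.868) = 80.7%.
- Design effect = 1 + 11 × 0.0183 = 1.2013, and 100 × 1.2013 gives 120.
- 120/0.85 = 141.2, so 142 per arm and 284 in total.

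The stated figure is reproduced, and it is the power for the plain between-arm difference. The effective size at follow-up is 142 × 0.85/1.2013 = 100.5, taken as 100 per arm.

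**Step 2: what the planned coefficient estimates.** In a regression of the 10-month score on arm and 4-month score, the arm coefficient is the 10-month difference minus the within-arm slope times the 4-month difference. With equal SDs the slope is ρ, so

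coefficient = d10 − ρ·d4

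SE = √[(1 − ρ²)(2/n)(1 + d4²/4)]

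The last factor allows for the correlation between arm and 4-month score that the treatment effect creates.

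Worked example with d4 = d10 = 0.40, ρ = 0.5, n = 100: coefficient = 0.40 − 0.20 = 0.20; SE = √(0.75 × 0.02 × 1.04) = 0.125; power = Φ(0.20/0.1249 − 1.960) = 36%.

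**Step 3: results at an effective 100 per arm.** The third scenario, with d10 = 0.20, is an assumed partial decay.

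| ρ | 0.40 then 0.40: coefficient, power | 0.48 then 0.42: coefficient, power | 0.48 then 0.20: coefficient, chance of significance for EUC |
|---|---|---|---|
| 0.3 | 0.28, 53% | 0.276, 51% | 0.056, 1% |
| 0.5 | 0.20, 36% | 0.18, 30% | −0.04, 5% |
| 0.7 | 0.12, 21% | 0.084, 12.5% | −0.136, 26% |
| 0.8 | 0.08, 15% | 0.036, 6% | −0.184, 56% |
| 0.9 | 0.04, 9% | −0.012, 2% | −0.232, 95.5% |

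Simulation (8,000 runs for each of six scenarios) agreed with these formulas. With the prior effects, the coefficient reaches zero at ρ = 0.42/0.48 = 0.875.

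If the 10-month effect is truly zero after d4 = 0.40, then at ρ = 0.6 the coefficient is −0.24 and the SE is √(0.64 × 0.02 × 1.04) = 0.115. The model then favours EUC in about Φ(0.24/0.1154 − 1.960) = 55% of trials.

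**Step 4: with baseline as the covariate.** Baseline is measured before randomization, so the coefficient equals d10. With no gain from the covariate, power is 80.7% for 0.40 and 84.4% for 0.42. With an assumed baseline-to-10-month correlation of 0.5 it is 90% and 93%.

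**Step 5: sensitivity to n.** Counting 120 independent patients per arm, with no design effect, the fully maintained case gives 42% at ρ = 0.5 (SE 0.114) and 17% at ρ = 0.8 (SE 0.079). The conclusion is unchanged.

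**The case against.** **Maintenance may mean what happens after month 4.** A model adjusted for the 4-month score does answer a recognised question: whether the arms diverge after the intervention ends. But H3, Table 5 and the aim stated in 5.6.C.ii all name the between-arm difference at 10 months. H3 also predicts significant improvement over usual care. In a model of later change, full maintenance sits near the null, so success would tend to appear as non-significance.

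**Baseline may enter anyway.** Section 5.6.C adds variables that differ between arms at baseline. That only adds a covariate; the 4-month score stays. With d4 = d10 = 0.40, ρ = 0.7 and the other two correlations at 0.5, the partial slope is (0.7 − 0.25)/0.75 = 0.6. The coefficient is then 0.40 − 0.6 × 0.40 = 0.16, with a simulated power of 34%.

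**The growth model covers the 10-month contrast.** Section 5.6.C.iii plans a three-time-point mixed model that does not condition on the 4-month score, so the contrast would not go wholly unexamined. That model is labelled exploratory and starts from a linear trend. It is not the H3 test.

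**The size rests on an assumed correlation.** This stands. At ρ = 0.3, power with full maintenance is 53%, so a non-significant result becomes the likelier outcome only at moderate ρ and above. With equal SDs, full maintenance dilutes the coefficient without reversing it; a wrong sign requires d10 < ρ·d4, meaning some decay or a very high ρ. The plan also gives no rule for reading a non-significant H3, so the conclusion that benefit was not maintained is the likely reading rather than a prescribed one.

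**The damage is limited.** H2 is correctly specified, and the sample size is set on the post-intervention effect. The error is confined to H3.

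**Conclusion.** The concern holds. As written, the H3 model does not estimate the quantity that H3 and Table 5 define, and neither intention-to-treat analysis nor multiple imputation changes that. For any positive ρ combined with a 4-month benefit, the coefficient is pulled below the true 10-month effect; only the amount depends on assumptions. At an effective 100 per arm and ρ between 0.5 and 0.8, power is 36% to 15% for a fully maintained effect of 0.40 and 30% to 6% for the plan's prior effects. The 80% in 5.6.A therefore does not apply to this model. Partial or complete loss of benefit can produce a significant result against EPIC. This should be corrected before analysis, because it concerns a named hypothesis on both primary outcomes.

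**What to change.** In 5.6.C.ii, replace the post-intervention scores with the baseline scores, so that H3 uses the same baseline-adjusted ANCOVA as H2 with the 10-month outcome. A repeated-measures model with categorical time and baseline adjustment, from which the 10-month contrast is taken, would serve equally well. If change after month 4 is of interest, keep the model adjusted for the 4-month score as a separately labelled secondary or exploratory analysis, and state that it does not test H3.

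The cost is one phrase. Table 10 already schedules HbA1c and DDS at baseline, and H2 already uses them, so no extra patients, visits or data are needed. The 80% power statement at the last follow-up then refers to the quantity being tested.
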